
	
Nonclinical data demonstrate that CO-1686 inhibits T790M as well as the common activating mutations (L858R, del19) and has minimal inhibitory activity towards WT EGFR at therapeutic doses. It is anticipated that CO-1686 will promote cell death in tumor cells with the T790M mutation, thus driving objective tumor responses and providing therapeutic benefit in patients who have developed T790M-mediated resistance to first generation EGFR inhibitors. Toxicities driven by WT EGFR inhibition should be minimal in treated patients.
 
The goals of this study are: (A) to evaluate the pharmacokinetic (PK) and safety profile of oral CO-1686; (B) to determine the maximum tolerated dose (MTD) and/or recommended Phase 2 dose (RP2D) of oral CO-1686; (C) to assess the safety and efficacy of CO-1686 in previously treated NSCLC patients known to have the T790M EGFR mutation.
 
CO-1686 was being developed with a companion diagnostic to identify patients whose tumors express activating EGFR mutations as well as the T790M resistance mutation. To evaluate alternative and less invasive procedures than tumor tissue biopsy to provide DNA, serial plasma samples from all patients will be analyzed for the presence of EGFR mutations including T790M in plasma. Patients will also have the option to provide serial urine specimens to determine whether EGFR mutations are detectable in transrenal nucleic acids.
 
The study was initiated in April 2012 using the free base form of CO-1686. Fifty-seven patients were treated with CO-1686 free base between April 2012 and August 2013. The highest dose of free-base CO-1686 administered was 900 mg BID; the MTD was not established. A hydrobromide (HBr) salt form of CO-1686 that has superior PK characteristics was introduced into the clinic in August 2013. CO-1686-HBr was tested at 500 mg BID, 625 mg BID, 750 mg BID, and 1000 mg BID in the dose escalation phase of the study. All doses tested had less than 33% incidence of dose limiting toxicities in Cycle 1. The dose of 750 mg BID was selected as suitable for further study and 2 expansion cohorts (Cohorts A and B) were opened at that dose level. Subsequently, as the Phase 1 data matured, the recommended dose was adjusted to 625 mg BID based on robust antitumor activity at lower doses and anticipated optimal tolerability.
 
RECIST responses have been observed across the range of doses studied in Phase 1. The current overall response rate in patients with T790M+ NSCLC is approximately 60%, based on a data cut from 40 patients in this study for the FDA end of Phase 2 meeting held in July 2014. The most common Grade 3 toxicity observed is hyperglycemia, occurring in approximately 30% of patients, which is most often managed with oral hypoglycemic monotherapy. Protocol Amendment 6 added dose levels of 500 mg BID and 625 mg BID to the Phase 2 cohorts to perform a comprehensive evaluation of dose and response and tolerability across multiple dose levels (Cohorts A and B), as well as an additional cohort (Cohort C – 625 mg BID regimen) to accommodate patients with a positive local T790M result but discrepant or inadequate central result. In Amendment 6, patients were to be allocated to the 500 mg or 625 mg BID regimens by 1:1 randomization.

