--	--

	
Amendment 7 made the following changes:
 

1. Clarification of CNS lesion exclusion criterion to ensure only patients with stable CNS disease are enrolled

2. Removal of the requirement for 1:1 randomization to the 2 dose levels. This will allow additional early experience to be gained at the recommended dose (625 mg BID) in order to support the Phase 2/3 program where studies are enrolling at 625 mg BID, as well as regulatory filings.

3. Allowing for a potential increase in the size of Cohort A. Experience to date shows that Cohort A (later line patients) enrolls more rapidly than Cohort B (second line patients). Amendment 7 allows enrolment to continue in Cohort A until Cohort B is fully enrolled. Based on current enrollment rates, the size of Cohort A will increase from 150 patients to approximately 275 patients.

4. Clarification that removal of 1:1 randomization allows patients to enroll in study before the central T790M status is obtained, in cases where the following conditions are met:

a. Have undergone a biopsy of either primary or metastatic tumor tissue within 60 days of dosing with study drug and have tissue available to send to the sponsor's lab or are able to undergo a biopsy during screening. No change (except for washout or dose adjustment if required to manage adverse effects) in antitumor therapy regimen is allowed between the biopsy and CO-1686 initiation (Study Inclusion Criterion 3);

 
AND
 

b. Local positive T790M result from biopsy taken at same time as central testing biopsy, with results available for sponsor review before enrollment

 

5. Clarification of requirements for continued treatment of patients who progress on CO-1686.

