Under Amendment 4, the RP2D initially identified in Phase 1 was to be the starting dose for patients enrolled into Phase 2. The RP2D was selected as 750 mg BID based on early efficacy data from the dose escalation portion of the study and patients are actively enrolling in cohorts A (later-stage) and B (earlier-stage disease) at 750 mg BID under Amendment 4. Subsequently, as the Phase 1 data matured, the recommended Phase 2 dose was adjusted to 625 mg BID based on robust antitumor activity at lower doses ([Figure 2](#)) and anticipated optimal tolerability. However, since an MTD was not reached in Phase 1 and the small sample size of each Phase 1 cohort, it was not possible to demonstrate a clear dose response for either efficacy or toxicity and consequently the recommended Phase 2 dose at 625 mg BID is an estimation. Amendment 6 allowed for the evaluation of 2 additional doses of CO-1686 (500 mg BID and 625 mg BID) in patients who have progressed on initial EGFR inhibitor therapy and in patients with later line disease. Amendment 7 allowed the sponsor to enroll the RP2D of 625 mg BID before the 500 mg BID dose in order to increase experience with the RP2D to support the ongoing Phase 2 and Phase 3 CO-1686 programs. In addition, Amendment 7 allowed the later-line patient population in Cohort A (more prevalent population) to continue enrollment as long as the earlier line patient population, Cohort B, is open for enrollment. Building on the observed efficacy of CO-1686, a more precise estimate of optimum dose will be derived from these expanded dose levels.

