no intervening chemotherapy between EGFR TKI and planned treatment with CO-1686. Amendment 6 expanded the size of cohorts A and B from up to approximately 40 patients each to approximately 190 patients each, and creates 1 additional cohort (Cohorts C with up to 100 patients), in order to assess safety and efficacy at 2 dose levels, and to compare ORR between dose levels. Cohort C (625 mg BID) consists of patients that fulfill eligibility for Cohorts A or B, has signed consent for the study, has a positive local T790M biopsy within 60 days of C1D1 but T790M negative or inadequate test by central laboratory. Patients will be allocated to the 500 mg BID or 625 mg BID dose levels as defined in [Section 7.2](#). Amendment 7 allowed the sponsor to enroll the RP2D of 625 mg BID before the 500 mg BID dose in order to increase experience with the RP2D in order to support the ongoing Phase 2 and Phase 3 CO-1686 programs. In addition, Amendment 7 allowed the later-line patient population in Cohort A (more prevalent population) to continue enrollment as long as the earlier line patient population, Cohort B, is open for enrollment. Patients will be able to enroll in Cohort C as long as the study is recruiting patients for the other cohorts and may contain up to approximately 100 patients.

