## **2.4 Sample Size**

Total number of patients – up to approximately 715 (Phase 1 N≈110; Phase 2 N≈605)

- Phase 1: CO-1686 free base (completed) - 57 patients  
CO-1686 HBr - approximately 53 patients
- Phase 2:
  - Cohort A: approximately 40 patients for dose level 750 mg BID, up to approximately 275 patients for combined dose levels of 500 mg BID and 625 mg BID
  - Cohort B: approximately 40 patients for dose level 750 mg BID, up to approximately 150 patients for combined dose levels of 500 mg BID and 625 mg BID
  - Cohort C: up to approximately 100 patients at 625 mg BID

For the initial MAA and NDA submissions all patients enrolled in this trial at a dose of 500mg BID or 625mg BID by the 31st of December 2014 with a data cutoff date of April 29, 2015 will be used for both efficacy and safety conclusions. All other patients treated in CO-1686-008 enrolled by the 31st of December 2014 have a data cutoff date of December 31, 2014. The efficacy and safety profile for CO-1686 will be established by the combined patients treated in this study and Phase 1 study, CO-1686-008.

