### 14.1 Adverse Events

Adverse events will be classified using the Medical Dictionary for Drug Regulatory Activities (MedDRA) classification system. The severity of the toxicities will be graded according to the NCI CTCAE whenever possible. Treatment-emergent adverse events (TEAEs) are defined as AEs with onset date on or after the date of first dose of study medication until the date of the last study medication dose plus 28 days. Adverse events will be considered treatment-emergent if all or part of the date of onset of the adverse event is missing and it cannot be determined if the adverse event meets the definition for treatment-emergent.

The number and percentage of patients who experienced TEAEs for each system organ class and preferred term will be presented. Multiple instances of the TEAE in each system organ class and multiple occurrences of the same preferred term are counted only once per patient. The number and percentage of patients with at least one TEAE will also be summarized.

Separate tables will be presented as follows:

- All TEAEs;
- TEAEs by CTCAE grade;
- Grade 3 or greater TEAEs;
- Treatment-related TEAEs;
- Serious TEAEs;
- Serious treatment-related TEAEs;
- TEAEs with an outcome of death;
- TEAEs leading to discontinuation of study medication; and
- TEAEs resulting in reduction, delay, or interruption of study medication
- Time to the first adverse event that results in a reduction, interruption or discontinuation of study drug.

The incidence of TEAEs will be summarized by relationship to study drug according to the following categories: “treatment-related,” or “not treatment-related”. The category of treatment-related is defined as a relationship of “Possible/Probable”, “Definitely”, or missing. If a patient experiences multiple occurrences of the same AE with different relationship categories, the patient will be counted once, as a relationship category of treatment related.

If a patient experiences multiple occurrences of the same AE with different toxicity grades, the patient will be counted once for the maximum (most severe) toxicity grade. AEs with a missing toxicity grade will be presented in the summary table with a toxicity grade of “Missing.” For each toxicity grade, the number and percentage of patients with at least one TEAE of the given grade will be summarized.

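### Dose groups can differ in follow-up in either direction, yet the general adverse event tables and ORR are crude percentages with no common window or exposure denominator

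*SAP*

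**What the plan says.** **Cutoffs.** SAP 2.4 takes the patients enrolled at 500 or 625 mg BID by the end of 2014 and says that this set "with a data cutoff date of April 29, 2015 will be used for both efficacy and safety conclusions". All other patients enrolled by then "have a data cutoff date of December 31, 2014". SAP 15 repeats the April date for the first set but does not mention the earlier cutoff. SAP 3 builds the summary tables from all treated patients, lets selected dose groups from both phases be shown, and allows Fisher's exact test between groups it calls randomised.

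**Allocation.** The protocol synopsis lists among the Amendment 7 changes: "Removal of the requirement for 1:1 randomization to the 2 dose levels". The section on RP2D selection adds: "Amendment 7 allowed the sponsor to enroll the RP2D of 625 mg BID before the 500 mg BID dose".

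**Aim.** Amendment 6 added two doses to Phase 2 "to perform a comprehensive evaluation of dose and response and tolerability across multiple dose levels" (synopsis), and it enlarged Cohorts A and B "in order to assess safety and efficacy at 2 dose levels, and to compare ORR between dose levels" (Protocol 5.1.3). Protocol 11.2.10.2 tabulates adverse events by dose group.

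**Summaries.** SAP 14.1: "The number and percentage of patients who experienced TEAEs for each system organ class and preferred term will be presented". SAP 11.1 gives ORR as counts and percentages. SAP 8 describes exposure separately and never uses it as a denominator. Among the safety and response outputs, three use follow-up time: time to the first adverse event leading to a dose change or discontinuation (SAP 14.1), time to the first glucose-lowering medication (SAP 14.2) and duration of response (SAP 11.2.1). SAP 11.3.2 and 11.3.6 describe only how long patients were treated.

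**The concern.** The percentage of patients who have ever had an event rises with the time they are watched. Two features of the plan can make that time differ between doses. The split cutoff separates 500 and 625 mg BID from 750 mg BID, 1000 mg BID and free base. The permitted enrolment order can separate 500 from 625 mg BID at their shared cutoff. Nothing in the design balances either one, because allocation is not randomised.

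The tables most readers will use to compare doses are the general adverse event tables and the ORR table. Neither has a common window, a minimum follow-up rule or an exposure denominator. A difference in those tables could partly reflect accrual order and cutoff date, and these tables feed the efficacy and safety conclusions of a marketing submission.

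**Working it through.** **Inputs.** Cutoffs, enrolment limit and cohort sizes: SAP 2.4. Scan schedule and 21-day cycles: SAP 2.3.1. Start of Phase 2 at 750 mg BID: February 2014 in Protocol 5.1.3 (the synopsis says January). Timing of hyperglycemia: Protocol 7.4.3. The documents give no event hazards, no Amendment 6 or 7 dates and no follow-up by dose, so the inputs marked as assumed below are mine.

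**1. The plan's own total.** 57 + 53 = 110; 40 + 275 + 40 + 150 + 100 = 605; total 715, as SAP 2.4 states.

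**2. Cutoff gap.** 31 December 2014 to 29 April 2015 = 31 + 28 + 31 + 29 = 119 days, or 119/21 = 5.67 cycles.

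**3. Direction.** Patients who start on the same day have 119 days more potential follow-up at 500/625 mg BID. A 500/625 mg BID patient who starts exactly 119 days after a patient in another group has the same follow-up; a later start gives less. A 750 mg BID patient starting on 1 February 2014 has 333 days, so the break-even start is 31 May 2014. With an assumed 1 August 2014 start at 500/625 mg BID:

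| Rule | 750 mg BID, 1 Feb 2014 | 500/625 mg BID, 1 Aug 2014 | Difference |
|---|---|---|---|
| Cutoffs as in SAP 2.4 | 333 | 271 | 62 days |
| All at 29 April 2015 | 452 | 271 | 181 days |
| All at 31 December 2014 | 333 | 152 | 181 days |

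**4. Effect on event percentages (assumed hazards).** Give both groups the same hazard h = -ln(1 - r)/365.25 for one-year risk r. With discontinuation at rate m, crude incidence by time t is h/(h + m) × (1 - exp(-(h + m)t)). Take 119 versus 238 days:

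| One-year risk r | No discontinuation (m = 0) | Median 180 days on drug (m = ln 2/180) |
|---|---|---|
| 10% | 3.4% v 6.6% | 2.7% v 4.4% (1.7 points) |
| 30% | 11.0% v 20.7% | 8.8% v 13.8% (5.0 points) |
| 50% | 20.2% v 36.3% | 16.4% v 24.6% (8.3 points, unrounded inputs) |

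The true risk is identical in every pair. A rate per unit of time on drug, or incidence by a fixed day, would show no difference.

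**5. Early events.** If an assumed 80% to 95% of events occur by Day 21 with exponential onset, 99.0% to 99.98% have occurred by Day 60. Beyond about 60 days of follow-up the artefact nearly vanishes.

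**6. ORR, 500 versus 625 mg BID.** The Cycle 2 and Cycle 4 scans fall on Days 35-42 and 77-84. The last patient allowed into this set has 119 days, so both scans are reachable. If an assumed 5% to 15% of responders first respond after Cycle 4, and true ORR is 40% to 60%, the largest artefact is 0.40 × 0.05 = 2 points to 0.60 × 0.15 = 9 points. That extreme needs one group cut off entirely at Cycle 4 and the other followed fully.

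**The case against.** Several counterarguments are sound, and they limit the point.

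- **The 119-day gap does not touch 500 versus 625 mg BID.** A reader might infer that it does. Both doses share the April cutoff, and SAP 2.4 rests the conclusions on that set. The gap matters only where other doses are shown beside it.
- **The SAP does not rely only on crude percentages.** Three outputs use follow-up time, one of them in SAP 14.1 itself. They do not repair the general adverse event or ORR tables. Nor does the confirmed-response rule in SAP 11.1: it sets undetermined patients aside as inevaluable, so its denominator also depends on follow-up.
- **The direction is unknown.** It is tempting to say that the groups with the earlier cutoff will look safer. Those groups also largely started earlier, and step 3 shows that the split cutoff can narrow the difference. For the same reason, moving everyone to one cutoff is not a safe remedy. On the assumed dates it widens 62 days to 181.
- **Enrolling 625 mg BID first was permitted, not reported as done.** There are offsets: the set includes Phase 1 patients, whose HBr escalation began at 500 mg BID and listed 625 mg BID last (Table 9), and Cohort C, at 625 mg BID only, stayed open while other cohorts recruited.
- **The best-known toxicities come early.** Protocol 7.4.3 places hyperglycemia generally in the first 3 weeks, and Protocol 3.4.1 places QTc onset between Days 1 and 15. A reader might offer Grade 3 or higher cataracts (12 + 9 + 7 = 28 of 635 in Appendix D, Table 1) as a late event. That table gives no onset times and pools doses, so it does not show this.

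What stands is that the two main summaries have no version free of follow-up time, while comparing doses remains a stated aim.

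**Conclusion.** The point holds as a gap in the analysis, not as a demonstrated bias. Potential follow-up can differ between dose groups in either direction. The general adverse event tables and ORR offer no summary that removes the difference.

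The 119 days is exact. Every percentage-point figure is an illustration on assumed hazards, time on drug and late-response shares: 1.7 to 8.3 points for events that accrue steadily, near zero for events concentrated in the first weeks, and at most about 2 to 9 points for ORR between 500 and 625 mg BID. The documents do not support saying which dose is favoured. The change is worth making because it is cheap and works whichever way the imbalance runs.

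**What to change.** Keep the cutoffs in SAP 2.4. Then:

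1. **SAP 2.4 and 8:** state each group's cutoff in the tables, and report potential follow-up and exposure by dose group.
2. **SAP 14.1:** in any table that shows doses side by side, add the treatment-emergent adverse event incidence within Days 1-84 and events per patient-month on drug. Count events over the same time that forms the denominator.
3. **SAP 11.1:** in the same setting, add best response through the Cycle 4 scan.
4. **Who enters the landmark summaries:** patients first dosed at least 84 days before their own group's cutoff. All 500/625 mg BID patients in the submission set qualify (119 days or more). Elsewhere this means a first dose by 8 October 2014 (23 + 30 + 31 = 84 days to 31 December). Patients who stop treatment early stay in the denominator.

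The cost is SAP wording and a few extra columns, from data already collected under the plan. Rates per patient-month assume a roughly constant hazard, so they should sit beside the crude percentages and not replace them.

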### 3 GENERAL ANALYSIS CONVENTIONS

The summary tables will be presented for all patients treated with at least one dose of CO-1686 (safety population). Particular dose groups of interest, including patients from both Phase 1 and Phase 2, may be presented in the summary tables.

Quantitative variables will be summarized using descriptive statistics and may also be summarized categorically with frequencies and percentages. For variables registered on a continuous scale, the following will be presented: N, mean, standard deviation, median, minimum and maximum. Categorical variables will be presented using frequencies and percentages and the randomized treatment groups may be compared using Fisher's exact test. The Kaplan-Meier methodology will be used to summarize time-to-event variables. If estimable, the median together with a 95% confidence interval will be presented. The number of patients with events and the number of censored patients will also be presented.

All data will be used to their maximum possible extent but without any imputations for missing data.

Unless otherwise specified, baseline is defined as the last measurement on or prior to the first day of study drug administration.

### 4 ANALYSIS POPULATIONS

**PK-Evaluable Population**—all patients who have received at least one dose of CO-1686 and have had adequate PK assessments drawn for determination of the PK profile. Adequacy will be determined on a case-by-case basis and will be assessed prior to analysis of the blood samples.

**Food-Effect PK Population**—all patients participating in the food-effect PK evaluation in Phase 1 of the study who received CO-1686 on both Day -7 and Day 1 (Cycle 1) complied with the fed and fasted requirements, and have sufficient PK data for a comparison to be made between the fasted and fed state.

**ECG/PK Comparison-Evaluable Population**—all patients in Phase 1 and Phase 2 who have received CO-1686 and have had adequate PK and ECG assessments performed for determination of the ECG effects and the relationship between PK and ECG

**Safety Population**—all patients who have received at least one dose of CO-1686.

**DLT-Evaluable Population**—all patients enrolled into Phase 1 of the study who received at least 80% of Cycle 1 scheduled doses of CO-1686 and completed Cycle 1 or who experienced a DLT in Cycle 1.

**Tumor-Evaluable Population**—all patients who received at least one dose of CO-1686, have measurable tumor lesions at baseline, and have at least one postbaseline disease assessment. Patients that died prior to receiving at least one postbaseline disease assessment will also be included.

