#### 7.4.1.3 Dose-limiting Toxicity

DLTs in Phase 1 are defined as any of the following events that occur during Cycle 1 (Safety and PK Assessment Period) in patients enrolled into a DLT evaluable cohort and are assessed by the investigator as probably, possibly or definitively related to CO-1686. Where applicable, events will be classified according to the National Cancer Institute Common Terminology Criteria for Adverse Events (NCI CTCAE) Version 4.0. Dose limiting toxicities include:

- Grade 3 or 4 skin eruption, nausea, vomiting, diarrhea or hyperglycemia despite the use of adequate/maximal medical intervention and/or prophylaxis
- Any Grade 4 skin rash/eruption with extensive superinfection requiring IV antibiotics and with life-threatening consequences (e.g., rash acneiform, papulopustular rash, Stevens-Johnson Syndrome)
- Any nonhematological CTCAE Grade 3 or greater AE (except alopecia, nausea, vomiting, diarrhea or hyperglycemia if well controlled by systemic medication)
- ANC  $< 0.5 \times 10^9/L$   $> 5$  days duration or febrile neutropenia (i.e., fever  $> 38.3^{\circ}\text{C}$  with ANC  $< 1.0 \times 10^9/L$ )
- Platelets  $< 25 \times 10^9/L$  or platelets  $< 50 \times 10^9/L$  with bleeding requiring a platelet transfusion
- Grade 4 anemia (life-threatening consequences, urgent intervention indicated)
- Delayed recovery from toxicity related to CO-1686 treatment that delays scheduled retreatment for  $> 14$  days

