#### 7.4.1.4 Definition of DLT-evaluable Patient

In order to be considered evaluable for dose-escalation decisions, a patient in Phase 1 must have:

- Received at least 80% of scheduled doses and have completed Cycle 1, Day 21, without a DLT, or
- Have experienced a DLT in Cycle 1

If a patient withdrew from the study without having met either of these criteria, then an additional patient was to be enrolled in that cohort.

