### Management of Hyperglycemia

CO-1686 causes hyperglycemia in some patients and those with pre-existing diabetes may require more frequent monitoring and/or adjustments of diabetic medication. Clinical experience with CO-1686 suggests hyperglycemia generally occurs within the first 3 weeks of treatment, leading to the need for more intensive glucose monitoring during the first several weeks of the study. In order to minimize the risk of symptomatic hyperglycemia, the following schedule is recommended:

Fasting glucose will be measured at the following visits: Screening/baseline visit, Cycle 1/Day 1, Cycle 1/Day 4 ( $\pm 1$  day), Cycle 1/Day 8 ( $\pm 1$  day), Cycle 1/Day 15 ( $\pm 1$  day), Cycle 2/Day 1, Cycle 2/Day 15 ( $\pm 1$  day), Cycle 3/Day 1, Cycle 4/Day 1, Cycle 5/Day 1, etc. and End of Treatment visit.

The following guidelines for management of hyperglycemia have been developed by consulting an endocrinologist and based on experience in the Phase 1 study. Whilst the blood glucose thresholds for intervention outlined below should be followed, management of individual patients should be based on local practices and the treating physician's judgment. In all cases, the prescribing information should be followed and maximum approved dose of the anti-hyperglycemic agent should not be exceeded.

1. Additional monitoring outside of per protocol schedule is not needed if fasting glucose is less than 125 mg/dL ( $< 6.94\text{mmol/L}$ ).
2. If fasting glucose  $\geq 125$  mg/dL ( $\geq 6.94\text{ mmol/L}$ ) and  $\leq 160$  mg/dL ( $\leq 8.88\text{ mmol/L}$ ), patients will be asked to perform self-monitoring of blood glucose using finger stick blood testing. Tests should be performed at home once a day for 2 weeks, making note of time, fasted/fed state and glucose levels in a monitoring log provided. Patients should

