bring this monitoring log to scheduled visits and review with treating physician. If patient observes at home 2 or more fasting glucose measurements  $> 160 \text{ mg/dL} (> 8.88 \text{ mmol/L})$  and/or 2 or more random glucose measurements  $> 200 \text{ mg/dL} (> 11.01 \text{ mmol/L})$  (or a combination of the two) before their next scheduled clinic visit, they should call their health care professional (HCP), inform the study site and schedule a visit as soon as possible with the treating physician. If glucose  $> 160 \text{ mg/dL} (> 8.88 \text{ mmol/L})$  (fasting) or  $> 200 \text{ mg/dL} (> 11.01 \text{ mmol/L})$  (random) is confirmed, then start treatment with metformin or anti-hyperglycemic agent of choice (See [Figure 8](#)).

[figure not shown]
3. If fasting glucose  $> 160 \text{ mg/dL} (> 8.88 \text{ mmol/L})$  and  $< 250 \text{ mg/dL} (< 13.87 \text{ mmol/L})$  on more than 2 occasions, start metformin or anti-hyperglycemic agent of choice. Patients should perform self-monitoring of blood glucose using finger stick blood testing. Tests should be performed at home once a day, making note of time, fasted/fed state and glucose levels in a monitoring log provided. Patients should bring this monitoring log to scheduled visits and review with treating physician.
4. If fasting glucose  $\geq 250 \text{ mg/dL} (\geq 13.87 \text{ mmol/L})$ , and the patient is not symptomatic, manage as for step 3 above. If the patient is symptomatic, then hold CO-1686 and bring glucose under control acutely, if necessary using insulin with conversion to metformin or anti-hyperglycemic agent of choice once plasma glucose is controlled. Once patient is asymptomatic and deemed appropriate for additional therapy, CO-1686 may be re-introduced at a reduced dose, with concomitant metformin/anti-hyperglycemic agent of choice. Patients should perform self-monitoring of blood glucose using finger stick blood testing. Tests should be performed at home twice a day, before breakfast and before dinner, making note of time, fasted/fed state and glucose levels in a monitoring log provided. Patients should bring this monitoring log to scheduled visits and review with treating physician.

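### The DLT-evaluable rule ignores why Cycle 1 doses were missed, so a drug-related hold of about 4.5 to 14 days without a DLT leaves both numerator and denominator

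*SAP*

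**What the plan says.** SAP section 4 defines the DLT-evaluable population as Phase 1 patients "who received at least 80% of Cycle 1 scheduled doses of CO-1686 and completed Cycle 1 or who experienced a DLT" in that cycle. Protocol 11.1 carries the same definition. Protocol 7.4.1.4, which governs escalation decisions, sets the same two routes: "Received at least 80% of scheduled doses and have completed Cycle 1, Day 21, without a DLT, or" a DLT in Cycle 1. Replacement there is tied to withdrawal: "If a patient withdrew from the study without having met either of these criteria, then an additional patient was to be enrolled in that cohort".

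Protocol 7.4.1.3 decides what counts as a DLT. The general Grade 3-or-worse criterion has a carve-out: "except alopecia, nausea, vomiting, diarrhea or hyperglycemia if well controlled by systemic medication". Grade 3 or 4 hyperglycemia that persists despite adequate treatment remains a DLT. A delay is a DLT in its own right only when long: "Delayed recovery from toxicity related to CO-1686 treatment that delays scheduled retreatment for" more than 14 days.

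For a fasting glucose of 250 mg/dL or more, Protocol 7.4.3 says: "If the patient is symptomatic, then hold CO-1686 and bring glucose under control acutely". It gives no length for the hold. The same section notes that "hyperglycemia generally occurs within the first 3 weeks of treatment", and the DLT window is 21 days.

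Protocol 3.4.1, which reports the DLT results, describes the evaluable set differently: patients who finished Cycle 1 and were enrolled while escalation was running. It mentions no dosing threshold.

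**The concern.** The rule lets an outcome that the drug can cause decide who is in the denominator. A patient who could not take the dose because of toxicity, but whose event falls short of every DLT criterion, is treated like one who missed doses for an unrelated reason. If that patient stays on study, the text does not call for a replacement either.

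This is plausible for this drug. Protocol 3.4.1 names hyperglycemia as the most frequent DLT, it tends to appear within the DLT window, and controlled cases are exempt from the Grade 3 criterion.

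DLT incidence is a Phase 1 primary endpoint, and Protocol 11.2.10.2 promises a DLT table by dose group. The statements that every dose was below 33% and that no MTD was reached are part of the Phase 2 dose rationale (Protocol 3.5.3, 5.1.2, 7.4.1.5), and the SAP supports the NDA and MAA. SAP section 15 already returns patients who died before their first scan to the efficacy set. The DLT set has no comparable correction.

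**Working it through.** **1. Where the gap lies.** Inputs: 21-day cycle, 80% threshold, 14-day delay clause. Doses needed = 80% of scheduled doses, rounded up.
- QD: 0.8 × 21 = 16.8, so 17 needed; fails at 5 or more missed.
- BID: 0.8 × 42 = 33.6, so 34 needed; fails at 9 or more missed (4.5 days).
- TID: 0.8 × 63 = 50.4, so 51 needed; fails at 13 or more missed.

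The affected group on BID dosing is a drug-related hold of at least 4.5 and at most 14 days with no other DLT criterion met. A shorter hold leaves the patient in as non-DLT. A longer delay, or any DLT, leaves the patient in as a DLT.

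**2. Can the number be recovered?** No. No count of patients failing the 80% rule is given, and Table 1 (DLTs by dose level) was not in the text available for this review. One comparison shows that the denominators are unclear. Table 3 has 1 treatment-related glucose event among 12 patients at 625 mg BID (8%), yet Protocol 3.4.1 reports hyperglycemia DLTs of 11% to 25% at every HBr level. One event gives 11% only with 9 or fewer evaluable (1/9 = 11.1%; 1/10 = 10%). Expansion patients (Protocol 7.4.1.7), unfinished cycles or different data cut-offs could explain this, so it is not evidence that the 80% rule removed anyone.

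**3. Effect on crude rates (assumed counts).** Starting fractions are chosen to match the reported 11% and 25%, which are hyperglycemia DLT frequencies, not total DLT rates. Each line gives the result with restored patients counted as not tolerating, then as non-DLT.
- 1/9 (11.1%), one restored: 2/10 = 20.0%, or 1/10 = 10.0%.
- 1/9, three restored: 4/12 = 33.3%, or 1/12 = 8.3%.
- 2/8 (25%), one restored: 3/9 = 33.3%, or 2/9 = 22.2%.
- 1/4 (25%), one restored: 2/5 = 40%, or 1/5 = 20%.

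**4. Effect on an escalation decision.** Protocol Appendix C gives logit θ(d) = α + β·d/100, with α ~ N(−4, 2²), β ~ N(0.1, 0.25²), and half a pseudo-observation at the lowest dose (no DLT) and at the highest (half a DLT). A dose is barred when the probability that its DLT rate exceeds 33% is above 50%. A grid posterior, with 500 and 2250 mg/day as the end doses, first reproduces the appendix example and then adds one patient.
- Table 4.2 (1 DLT in 5 at 1000 mg/day): probability that 1250 mg/day is safe is 0.562, against 0.558 printed. Adding one patient at 1000 mg/day as not tolerating (2/6) gives 0.304, so 1250 mg would not open. Added as non-DLT (1/6), it is 0.634.
- Table 4.4: probability that 1500 mg/day is safe is 0.533, against 0.538 printed. Adding one patient at 1250 mg/day gives 0.324 or 0.595.

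These are the appendix's illustrative data, not trial results. They show that one patient can decide a step at these cohort sizes, and that the sign depends on how that patient is counted.

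**The case against.** The strongest reply is that the reported results may not use this rule. On the wording of Protocol 3.4.1, a held patient who finished Cycle 1 is already in the denominator as non-DLT. That stands, and it means the statements about 33% and the MTD cannot be said to rest on the 80% set. It also leaves two definitions of one population that need reconciling.

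Other points also stand.
- The hyperglycemia guidance was written from Phase 1 experience, and nothing shows that its hold instruction applied before escalation ended in January 2014.
- Hyperglycemia severe enough to stop dosing might be judged not well controlled, and so be a DLT.
- The documents do not say whether a dose withheld on instruction is still a scheduled dose; if it is not, the patient may remain evaluable.
- These patients stay in the safety population. SAP 14 tabulates events leading to dose reduction, delay or interruption, and SAP 5 gives population allocation.
- The SAP's own table list contains no DLT table.

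A reader might infer that every toxicity hold, or every hold for controlled hyperglycemia, removes a patient. Step 1 of the working shows otherwise. A reader might also infer that the rule biases the DLT rate downward, or that some dose really exceeded 33%. The documents support neither: the direction depends on how restored patients are counted, and no affected patient is identified.

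The reply does not remove the mechanism. Three sections state the rule without regard to cause, and population counts without reasons do not show who was lost to toxicity.

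**Conclusion.** The point holds in limited form. As written, the rule removes from the DLT rate a Phase 1 BID patient held for drug-related toxicity for about 4.5 to 14 days of Cycle 1 who meets no other DLT criterion. This assumes that withheld doses count as scheduled and that the 14-day clause covers holds within a cycle. The size is unknown and may be zero. With small cohorts, one such patient could move a rate or an escalation step either way. Escalation is complete and its decisions cannot be changed, so this is a worthwhile reporting correction. It does not show that the Phase 1 conclusions are wrong.

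**What to change.** - In SAP section 4, exclude a patient for under 80% dosing only when the missed doses were not due to CO-1686-related toxicity, and say whether withheld doses count as scheduled.
- Reconcile Protocol 3.4.1 with Protocol 7.4.1.4, Protocol 11.1 and SAP 4, and state which set produced the reported DLT rates.
- Give, by dose level, the number of Phase 1 patients who failed the 80% rule and the reason.
- Report the DLT rate by dose under the protocol rule. Beside it, as a labelled post hoc sensitivity analysis, keep toxicity-held patients in the denominator, once as non-DLT and once as not tolerating the dose.
- Qualify the below-33% and MTD-not-reached statements if they do not hold under both counts.

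The DLT definition and the clinical hold rules stay unchanged. The cost is SAP wording and one table from dosing and adverse event data already collected. The upper-bound DLT rates may look less favourable.
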